7.5. Physical Examination

Physical examination will be listed only.

8. PHARMACOKINETIC ANALYSIS

8.1. Drug Concentration

The observed values of APL-2 concentrations will be evaluated using the PK population. APL-2 concentrations will be summarized by disease groups at each scheduled time point using descriptive statistics. Moreover, APL-2 concentrations will be summarized by disease groups (if at least 2 subjects within a particular disease group) and dose groups at each scheduled time point using descriptive statistics. In addition, APL-2 concentrations will be summarized by dose groups across all patients at each scheduled time point using descriptive statistics (including at least mean, SD, CV, Min, Max, Geometric Mean/%CV). The number of subjects with a BLQ value will also be tabulated. The handling of BLQ in the summary table is described in Section 8.2.

Linear and log-linear individual concentration profile plots against the actual study visit will be produced by disease group with each subject being identifiable by disease group.

Linear and log-linear Mean (\pm SE) concentration plots against the actual study visit will be generated by disease group. The number of subjects contributing to each median value at a visit will be presented above the x-axis.

A listing of concentration data will be presented by disease group and dose. The actual time, deviation, and percent deviation from nominal time will be listed.

All summaries and analyses of the pharmacokinetic data will be based on the Pharmacokinetic Population defined in Section 4.4.

8.2. Handling BLQ Values

APL-2 concentrations reported as below the limit of quantification (BLQ) will be taken as zero for linear plots, and equal to the lower limit of quantification (LLOQ) for semi-logarithmic plots. For the computation of descriptive statistics, BLQ will be taken as zero, except for the calculation of the geometric mean where the LLOQ will be used.

Population PK and PD Modelling

In addition to the analyses outlined above, all PK and complement marker (PD) concentration data may be used to develop the population PK and exposure-response models in conjunction with other clinical study data. The methods and procedures will be described in a separate Analysis Plan if needed.

9. PHARMACODYNAMIC ANALYSIS

9.1. Pharmacodynamic Data

The PD endpoints will be evaluated using the PD Population.

Observed values, changes from baseline and percentage changes from Part A + B baseline and Part B baseline in C3, C3a, C4, C5a, AH50, CH50, and sC5b-9 will be summarized by disease group at each protocol specified time point using descriptive statistics for Part B and Part A + B. Moreover, this summary of PD parameters will be repeated by disease groups (if at least 2 subjects within a particular disease group) and dose groups at each scheduled time point using descriptive statistics for Part A and Part B. In addition, the above PD parameters will be summarized by dose group across all patients at each scheduled time point using descriptive statistics for Part B and Part A + B.

Individual observed values and individual changes from Part A + B baseline and Part B baseline will be presented graphically for each disease group. Actual sampling times will be used for the graphical presentation of individual data.

The mean $(\pm SE)$ of the observed values, mean changes from Part A + B baseline and Part B baseline, and mean percentage changes from baseline will also be presented graphically by disease group. Nominal sampling times will be used for the mean plots.

PD parameters will be listed together with changes from baseline and percentage changes from baseline by group.

10. OTHER ANALYSES

10.1. Immunogenicity

This data will be summarized in listing(s).

Statistical Analysis Plan 2.0 Protocol Number: APL2-201

11. INTERIM ANALYSIS

No interim analyses are planned.

12. SAFETY MONITORING COMMITTEE/REVIEW COMMITTEE

No SMC are planned for Part B.

13. DATA HANDLING CONVENTIONS

13.1. General Data Reporting Conventions

All statistical analyses will be performed using SAS® (Version 9.4 or higher, SAS Institute Inc., Cary, NC, USA).

Categorical variables will be tabulated as number of subjects and percentage of total number of subjects in the given analysis set as noted for each category. Percentages will be reported to one decimal place.

Descriptive statistics will be used to summarize continuous variables including number of subjects, mean, standard deviation (SD), median, minimum and maximum. Mean and median will be reported to 1 more decimal place than the raw data, while the SD will be reported to 2 more decimal places than the raw data. Minimum and maximum will be reported the same as the original data.

In general, all analyses will be performed for Part B and Part A + B unless otherwise specified. Subject specific listings will be provided by disease group, subject ID, Study Part and visit, if applicable.

13.2. Definition of Study Days

Part A + B: Study Day 1 for Part A + B will be the day a subject takes the first dose of APL-2, which will be calculated as:

For events that occurred on the day of or after administration of the first APL-2 dose:

Part A + B Study Day = visit date - date of first APL-2 dose + 1

For events that occurred on days before administration of the first APL-2 dose:

Part A + B Study Day = visit date – date of first APL-2 dose

Part B: Study Day 1 for Part B will be the day of first 1080 mg APL-2 dose during Part B, which will be calculated as:

For events that occurred on the day of or after administration of the first 1080 mg APL-2 dose in Part B:

Part B Study Day = visit date – date of first 1080 mg APL-2 dose + 1

For events that occurred on days before administration of the first 1080 mg APL-2 dose in Part B: Part B Study Day = visit date - date of first 1080 mg APL-2 dose

13.3. Definition of Baseline

Part A + B baseline: baseline is defined as the most recent non-missing measurement prior to or on the first administration of study drug in Part A (Study Day 1). Baseline can be the same date as first dose, given the measurement is expected prior to first dose when only date information is available.

Part B baseline: baseline is defined as the most recent non-missing measurement prior to or on the first administration of study drug during Part B.

13.4. Definition of Visit Windows

Data will be summarized and analyzed based on the list of visits specified in the schedule of assessments of the protocol. All the records post-baseline will be assigned to an appropriate analysis visit using the following:

- For the post-baseline visits, the lower and the upper bound for the analysis visit windows are defined as the midpoints of the target date of the scheduled visits.
- If the date of assessment falls in between the lower bound and the upper bound for a visit as specified in the schedule of assessments of the protocol, then it will be assigned to that visit.
- If the interval separating 2 scheduled visits is an even number of days, the middle day will be included in the lower bound of the next visit.
- If more than 1 record is within the same analysis visit window, the record closest to the midpoint of the interval will be used in the analysis.
- If 2 records are tied before and after the middle of the interval, the earlier record will be used in the analysis.

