- o Chemistry consists of BUN, creatinine (b), bilirubin (total and conjugated), uric acid, albumin, ALP, LDH, creatine kinase, AST, ALT, GGT, glucose, sodium, potassium, chloride, bicarbonate.
- p Vaccination serum samples (for antibody titer) will be collected prior to patient receiving vaccinations on that study visit.

07 July 2022

- q All PK collections will be taken predose for treatment visits and following ECGs at all other visits. Predose PK collections to occur within 1 hour before dose.
- r Patients who discontinue dosing will need to have ADA samples collected at 6 and 12 weeks after the last treatment. Patients who test positive for ADAs at any time will be followed up with ADA samples being collected every 6 months until the antibody levels revert to baseline.
- s Biomarkers for primary MN (PLA2R) and C3G (serum C3) should be collected for screening, while all secondary/exploratory disease-specific biomarkers should be collected throughout the treatment and follow-up period.
- t CKD-EPI creatinine equation (see https://www.niddk.nih.gov/); the CKD-EPI creatinine-cystatin C equation (if confirmation required).
- u Serum FSH to be performed on females only. Blood HIV, HCV, and HBsAg to be performed on all patients.

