### **10.1.** Transition to Twice-Weekly Dosing

Patients are able, at the discretion of the sponsor, to transition to twice-weekly dosing with 1080 mg pegcetacoplan prior to the Long-Term Extension Phase, but not earlier than Week 24. If a dose transition occurs during Part A, the subject will need to follow the dose transition visits, outlined in Table 2 below. Dose can be adjusted, as needed, to maintain clinical response.

Transition Visits (T1, T2, and T3) should be scheduled for 1, 2, and 4 weeks after the first day on which their dose was adjusted. Additionally, subjects should be instructed to skip their Core Study Phase dose the day before the visit at which their dose will transition.

**Table 2:** Part A, Dose Transition Visits

		Dose Transition Visits	
Study Week	T+1W	T+2W	T+4W
Study Day	T+7D	T+14D	T+28D
Study Visit	T1	T2	Т3
Visit Window (±Days)	2	2	2
Physical examination a			
Triplicate 12-lead electrocardiogram			
Pegcetacoplan administration b	X	X	X
Injection site assessment c	X	X	X
Concomitant medications	X	X	X
Vital sign measurements d	X	X	X
Urinalysis	X	X	X
Return uPCR samples		X	X
Bloode	X	X	X
Pharmacokinetics f	X	X	X
Antidrug Ab assays g			X
Hematology and chemistry	X	X	X
PD for Complement profile f	X	X	X
Pregnancy (β-HCG and FSH)			
Urine pregnancy test h			X
Adverse events	X	X	X
Drug Dispensation for Home Administration	X	X III. in a sign of a	X

Abbreviations:  $\beta$ -HCG = beta human chorionic gonadotropin; ECG = electrocardiogram; IP = investigational product; PD = pharmacodynamic; PI = primary investigator; SC = subcutaneous; uPCR = urine protein-to-creatinine ratio; WOCBP = women of childbearing potential.

- a Symptom-driven physical examinations may be performed at unscheduled time points if deemed necessary by the PI.
- b Subjects will self-administer SC pegcetacoplan, after receiving appropriate training by a research nurse or other personnel. During site visits subject will self-administer pegcetacoplan at the site if the visit occurs on a dosing day. If the visit falls on a nondosing day, no IP administration is needed.
- c Between site visits, subjects will be instructed to report any injection site reaction to the study coordinator.

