6. EFFICACY ANALYSES

Unless otherwise stated, all efficacy analyses will be summarized per disease groups (C3G and IgAN) by analysis visit (see Section 13.4). For subjects from the other disease group, all efficacy data will be listed in the listings.

No formal inferential statistics will be applied to data collected in the study.

The following plots with $(\pm SE)$ error bars will be provided for primary and secondary efficacy endpoints outlined below over time based on the analysis visit (see Section 13.4) per disease group:

- Mean with individual subject plots overlaid
- Percentage change from baseline with individual subject plots overlaid

Where applicable, the area for ULN and LLN will be shaded on each graph. Also, the number of subjects contributing to each mean value at a visit will be presented above the x-axis.

In addition, plot with (±SE) error bars will also be provided for percentage change in mean uPCR.

The primary and secondary efficacy endpoint analyses will be performed for both the ITT Population and Per Protocol Population. Exploratory analysis will only be performed for the ITT Population. In addition, when ITT Population is the same as Per Protocol Population, data will only be presented by ITT Population.

Change from baseline are defined as change from Part B baseline and change from Part A + B baseline, which are:

Part A + B baseline: baseline is defined as the most recent non-missing measurement prior to or on the first administration of study drug in Part A (Study Day 1). Baseline can be the same date as first dose, given the measurement is expected prior to first dose when only date information is available.

Part B baseline: baseline is defined as the most recent non-missing measurement prior to or on the first administration of study drug during Part B.

For categorical data, proportions will be based on the number of subjects who have the opportunity to be assessed at that visit.

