6.2. Analysis of Secondary Efficacy Endpoints

Changes from Part A + B baseline and Part B baseline and percentage change from Part A + B baseline and Part B baseline will be summarized in the same fashion with the primary efficacy endpoints for following endpoints:

Statistical Analysis Plan 2.0 Protocol Number: APL2-201

- eGFR
- Complement biomarkers including serum C3, C3a, C4, C5a, AH50, CH50, and sC5b-9 (see Section 9.1)
- Serum albumin

Additional disease parameters and/or biomarkers may also be analyzed.

eGFR will be calculated using CKD-EPI (2021) formula as:

 $eGFR = 141 \text{ x} \min(SCr/K, 1)^{a} \text{ x} \max(SCr/K, 1)^{-1.209} \text{ x} 0.993^{Age} \text{ x} 1.018 \text{ [if female]x} 1.159 \text{ [if black]}$

where SCr is standardized serum creatinine in mg/dL, K is 0.7 for females and 0.9 for males, a is -0.329 for females and -0.411 for males.

In addition, stabilization or improvement in eGFR from baseline, which is defined as GFR no more than 25% less than the baseline, will be tabulated by analysis visit including the following categories:

- Stable GFR: no more than 25% (+/-) change
- Improvement in GFR: >25% increase
- Worsening of GFR: >25% decrease
- Stabilized or Improved eGFR: <=25% decrease

Complete clinical remission, defined as normalization of proteinuria as defined by < 200 mg/g uPCR, will be tabulated by visit.

In addition, a responder analysis summarizing those patients with uPCR < 500 mg/g by each visit will be provided as well as a responder analysis by visit summarizing those patients with a uPCR reduction from baseline by 30% and 50%. However, subjects who have missing data, or have taken prohibited med, or received dialysis or renal transplant will be identified as non-responder.

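### SAP 2.0 section 13.4 keeps the record nearest the window midpoint rather than the target day, so a Part A transition-visit chemistry sample can stand in for Week 48; separately, the Week 48 24-hour urine window and interval disagree

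*SAP*

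**What the plan says.** SAP 13.4 first sends every record to a window: "All the records post-baseline will be assigned to an appropriate analysis visit using the following". Where a window holds several, "If more than 1 record is within the same analysis visit window, the record closest to the midpoint of the interval will be used", and a tie on either side of the middle goes to the earlier record. In 13.4.3 the Part A row for Week 48 has target day 336, window 315 - < 343 and interval 28. T1, T2 and T3 have rows in the Part B table for subjects who transition in Part B, but none in the Part A table.

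Protocol 10.1 lets a subject move to twice-weekly dosing "prior to the Long-Term Extension Phase, but not earlier than Week 24". Transition visits "should be scheduled for 1, 2, and 4 weeks after the first day on which their dose was adjusted", each with a ±2-day window. Protocol Table 2 marks "Hematology and chemistry" at all three. Footnote o to the Schedule of Events reads: "Chemistry consists of BUN, creatinine (b), bilirubin (total and conjugated), uric acid, albumin", and continues with further analytes. Table 2 has no eGFR row, but SAP 6.2 derives eGFR from serum creatinine ("eGFR will be calculated using CKD-EPI (2021) formula as"), so a transition chemistry sample is enough to produce one.

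SAP 6 and 7.2 summarize efficacy and laboratory data by analysis visit. In SAP 13.4.1 the Part A Week 48 row for 24-hour urine has target 336, window 2 - < 343 and interval 14.

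**The concern.** A window built from the midpoints between neighbouring visits is centred on its target only when the gaps on both sides are equal. At Week 48 they are not: the previous visit is 42 days earlier and the next is 14 days later. Choosing by distance to the window's centre then favours records taken about a week before the visit that the row is named after. Protocol-planned transition samples can fall there, so no unscheduled sample is needed.

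At stake is the Week 48 entry for albumin, creatinine-based eGFR and its stable/improved/worsened category, and the safety laboratory values, in the Part A + B tables. For an affected subject the row would show a sample taken shortly after a regimen change, and Visit 15 would be left out of it.

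The 24-hour urine row is a separate inconsistency. Its printed interval cannot be the width of its printed window, and a programmer has to guess which one governs.

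**Working it through.** **Week 48 window, other endpoints (SAP 13.4.3).** Target days from the Schedule of Events: Visit 14 = 294, Visit 15 = 336, Visit 16 = 350.

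- Lower bound: (294 + 336)/2 = 315. Upper bound: (336 + 350)/2 = 343. Width: 343 − 315 = 28. All three agree with the SAP.
- Midpoint: (315 + 343)/2 = 329, or (315 + 342)/2 = 328.5 if only days inside the window count.
- Day 336 lies 7 days (329) or 7.5 days (328.5) from the midpoint. Every day from 322 to 335 is at least as close under 329, with the tie at Day 322 going to the earlier record, and strictly closer under 328.5.

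**Switch at a scheduled visit, nominal days.** T1, T2 and T3 fall 7, 14 and 28 days after the switch.

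| Switch at | T1 | T2 | T3 | In Week 48 window (315-342)? |
|---|---|---|---|---|
| Visit 11, Day 168 | 175 | 182 | 196 | no |
| Visit 12, Day 210 | 217 | 224 | 238 | no |
| Visit 13, Day 252 | 259 | 266 | 280 | no |
| Visit 14, Day 294 | 301 | 308 | 322 | T3 only |

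For Visit 14, T3 on Day 322 is 7 days from midpoint 329. That ties with Visit 15, so T3 is kept as the earlier record. With midpoint 328.5 it is 6.5 against 7.5 days, and T3 wins outright. The value used is then 336 − 322 = 14 days older than Visit 15.

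**Visit 14 switch with ±2-day windows.** Let s be the sum of the Visit 14 and T3 shifts, so T3 is on Day 322 + s. The values s = −4, …, 4 arise in 1, 2, 3, 4, 5, 4, 3, 2, 1 ways. Let e be the Visit 15 shift.

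- Midpoint 329: T3 is kept when 7 − s ≤ 7 + e, that is s ≥ −e. For e = −2, −1, 0, 1, 2 the counts are 6 + 10 + 15 + 19 + 22 = 72 of 125.
- Midpoint 328.5: T3 is kept when 6.5 − s ≤ 7.5 + e, that is s ≥ −1 − e. The counts are 10 + 15 + 19 + 22 + 24 = 90 of 125.
- Target-day rule: T3 is at least 14 − 4 = 10 days from Day 336 and Visit 15 at most 2, so 0 of 125.

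**Switch at an unscheduled visit, nominal T days, Visit 15 on Day 336.** A transition record on Day 322-335 requires a start on Day 315-328 (T1), 308-321 (T2) or 294-307 (T3). Together these are Days 294-328, under either midpoint.

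**Week 24.** On nominal days a Visit 11 switch does not displace Visit 11. With T1 two days early (Day 173) it does: under midpoint (154 + 188)/2 = 171, T1 is 2 days away and Day 168 is 3. This is the same defect in a different row, and the same edit removes it.

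**24-hour urine, Part A Week 48 (SAP 13.4.1).**

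- Window 2 - < 343 has width 343 − 2 = 341, not 14. The Part B row 2 - < 252 prints 251 where subtraction gives 250; that convention would give 342 here.
- An interval of 14 would imply 329 - < 343. Protocol 14.1.7 allows the collection up to two weeks before Visit 15. With Visit 15 on Day 334-338, compliant days run from 334 − 14 = 320 to 338, so Days 320-328 would be lost.
- With the printed window the midpoint is 172 or 172.5. Under either, any sample on Day 9-335 would displace one on Day 336.

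**The case against.** The strongest case is that the consequence is small. The Part A endpoint analysis was produced under SAP 1.0, and SAP 2.0 words its efficacy endpoints as over time. Visit 15 ordinarily remains the Part B baseline (SAP 13.3), SAP 13.5 keeps every post-baseline value for flagging clinically significant results and for the listings, and nothing is tested. All of this stands. It limits the effect to one descriptive row.

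It can also be argued that the midpoint was meant to be the target day, or that summaries follow the scheduled visit list so that transition visits do not count. The text supports neither. The two days differ by about 7 at Week 48, and 13.4 sends all post-baseline records to a window. The repeat-assessment rule in 13.5 covers baseline, end of study and flagged values, not the choice for Week 48.

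A reader might infer that about a fifth of transitions are affected, since 35 of the 168 possible start days (168-335), or 21%, lead to displacement. The documents do not support that. Protocol 10.1 has the subject skip a dose on the day before the visit at which dosing changes, so a switch occurs at a visit, and only one scheduled visit leads to the problem. The other start days need an unscheduled switch visit. A reader might also extend the point to complement markers, but SAP 9.1 summarizes those at protocol-specified time points, so an effect there is not established.

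**Conclusion.** The point holds with a narrow reach. As written, 13.4 can report a T1-T3 chemistry value as Week 48 in the Part A + B tables of rollover subjects. For switches at scheduled visits this requires a switch at Visit 14. T3 then replaces Visit 15 on nominal days, and in 72 (midpoint 329) or 90 (midpoint 328.5) of the 125 in-window date combinations. These are counts of date patterns, not probabilities, and displacement is never certain. Unscheduled switches starting on Days 294-328 would also displace a Day 336 record.

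The documents do not say how many subjects switched at those times; the number may be zero. The Part A analysis under SAP 1.0 and the Part B baseline are not affected. Nor, in substance, is spot uPCR: its Week 48 window (329 - < 343) has midpoint 336 or 335.5.

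The 24-hour urine mismatch is real. No 24-hour collection is scheduled between Visit 3a and Visit 15, so it changes results only if unscheduled samples were taken. Protocol 16.2.2.1 says such samples are to be included.

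**What to change.** In the two selection rules of SAP 13.4, measure closeness and ties from the target day instead of the middle of the window. Add one sentence giving the scheduled visit's record priority over transition-visit or unscheduled records in the same window, or give Part A T1-T3 rows of their own. The priority sentence matters for unscheduled switches. With Visit 15 on Day 338, a transition record on Day 334-337 would still win under a target-day rule alone. T1-T3 values stay in the listings.

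In 13.4.1, make the Part A Week 48 row consistent in one of two ways:

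- keep 2 - < 343 and correct the interval to 341, or to 342 under the convention of the other rows starting at Day 2; or
- raise the lower bound to no later than Day 320, so that every compliant collection is covered, and report earlier unscheduled samples under their actual study day.

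The cost is two phrases, one priority sentence and one table cell, plus one reporting sentence if the lower bound is raised. It needs one programming change and no new data.

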13.4.1. Analysis Window for 24-hour Urine Collection

Pa	rt	A	+	B:
----	----	---	---	----

Part	Study visit	Mapped visit	Target day	Analysis window	Interval
Core Study Phase (Part A)	4	Day 1	1	1	1
	15	Week 48	336	2 - < 343	14

Part B:

Part	Study visit	Mapped visit	Target day	Analysis window	Interval
Long-Term Extension	15	Day 1	1	1	1
Phase (Part P)	17	Week 24	168	2 - < 252	251
(Part D)	19	Week 48	336	252 - < 420	168
	21	Week 72	504	420 - < 588	168

